Study Design	
This study will be a single site, prospective, randomized controlled clinical study. Approximately 40 individuals will be enrolled per the inclusion/exclusion criteria. Participants will be randomized using simple randomization into one of two arms. It is expected that study participants will be approximately equally distributed to either arm (20/20).
 
All interested, potential study participants will participate in the screening study phase. A member of the study team will seek informed consent and review inclusion and exclusion criteria to determine eligibility.
 
Individuals who qualify for enrollment will be randomized into one of two arms:
 
Arm A: Standard of Care + MR-Stride Plus Intervention Arm B: Standard of Care

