	
For all Study Participants, standard of care will be followed in both the acute care setting and in the discharge setting. Data required to evaluate the study objectives will be collected from record review and participant interviews. Participants will not be required to physically visit the study facility for study-specific procedures once they have been discharged from the acute care setting. Participants will be contacted by telephone to answer study assessment questions (e.g., mRS) intended at Days 45 (+/-2 Days), and 90 (+/-7 Days).
 
For those Study Participants enrolled into Arm A, study staff will review the intended walking intervention therapy schedule with the study participant. The Stride Plus is intended to be used for thirty (30) minutes a day, three (3) times a week. Participants will complete the following intervention phases related to use of the Stride Plus:
 
Intervention Phase 1 (within 24 hours from admission): In addition to standard of care therapy, study participants will complete at least one (1) walking therapy session with the Stride Plus while an inpatient in the acute care setting. Additional study therapy sessions will continue until the Study Participant is discharged from the acute care setting.
 
Intervention Phase 2 (Day 1 post-discharge to Day 90): In addition to standard of care therapy, study participants will complete a series of three (3) remote walking therapy sessions a week with the Stride Plus following discharge from acute care setting. Participants will schedule their sessions according to their preference and needs. Intervention Phase 2 will continue until the Study Participant is 90 days since discharge or earlier if the study participant is withdrawn from the study therapy. Participants will complete a walking test using the Stride Plus at discontinuation to determine the walking speed.
 
Post-Intervention Phase: Participants will be followed from discontinuation of the Stride Plus until Day 90. At Day 90 (+7 days), participants will complete a walking test using the Stride Plus to determine walking speed.
 
For those study participants in Arm B, the control group, only standard of care therapy will be provided. Participants will complete a 6-meter walk test (approximately 20 feet) to measure gait speed at baseline, biweekly post- discharge from acute care to day 90 (+/-7 days) following discharge.

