Procedures	
ARM A: STANDARD OF CARE + MR-STRIDE PLUS
 
For Study Participants randomized into Arm A, therapy sessions will begin within twenty-four (24) hours of enrollment. Intervention Phase 1 of the study requires a minimum of one (1) therapy session with the possibility of additional sessions until discharge; however, no more than 3 therapy sessions should occur during a given week. Intervention Phase 2 of the study requires 3 independent, remote therapy sessions a week regardless of discharge setting (e.g., rehabilitation hospital or home). Therapy will continue until day 90 (+/-7) following discharge from acute care. Therapy sessions with the MR-Stride Plus should not replace standard of care physical therapy, but be used in addition to standard of care physical therapy.
 
Participants may be contacted by the study staff to collect data on the number of standard of care physical therapy services provided and occurrence of readmission to acute care.
 
Participants will be able to schedule their three (3) sessions a week therapy according to their needs. Participants will be allowed to miss sessions if they are unable to make them up on a different day in the week. Participants therapy activity will be monitored remotely by the study team. If participants are unable to maintain the therapy schedule, the study will contact the participants to gauge willingness to continue. At investigator discretion and participant agreement, the number of sessions a week may be reduced or the participant may withdraw from therapy. If the participant is withdrawn from therapy, participants will be asked if they are willing to participate in a gait speed assessment using the MR-Stride Plus at day 45 and 90 post-discharge if they have not already been completed.
 
The 6-meter walk test (approximately 20 feet) will be conducted to evaluate gait speed at screening and biweekly thereafter until study completion. Gait speed will also be assessed at

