	
the time of withdrawal from study therapy if withdrawal occurs before Day 90 (+/-7) post discharge.
 
At the initial therapy session, Study Participants will be provided with all necessary equipment (pre set-up) and instruction for using the MR-Stride Plus. Study staff will provide appropriate oversight of the Participant during their initial walking therapy session in acute care to ensure safety; study staff will not be required to provide any instruction on use of the device. Participants will conduct 30 minutes of walking therapy at the participant's self-selected pace in a space (e.g., track or hallway) that limits the amount of stops and/or pivot turns in order to optimize velocity. Participants may choose to take breaks as needed, or when investigators believe that a rest break is necessary. The use of an overhead harness system is prohibited in this study. If technical or medical issues arise, the training session should be terminated to allow for adequate resolution.
 
For independent, remote therapy sessions following discharge from the acute care hospital, it is not required that a participant be under the supervision of clinical staff or a caregiver (depending on discharge setting), but participants may choose to according to their preference. Participants should perform their therapy sessions in an environment that limits safety hazards and, in a space, e.g., track or hallway, that limits the amount of stops and/or pivot turns in order to optimize velocity. Participants will perform their 30 minutes of walking therapy at their self-selected pace.
 
MR-Stride Plus Procedure: Study staff and participants will be required to follow the Instructions For Use (IFU) provided by MedRhythms. The IFU will detail all procedures required for proper operation of the system. Study Participants will be trained in utilizing the Stride Plus by the study staff. Mobile devices that have the MedRhythms Stride Plus application installed will be provided for use during therapy sessions. Participants will be provided with a pre-established username and password. No personally identifiable patient information will be recorded or stored in the Stride Plus application.
 
ARM B: STANDARD OF CARE
 
For Study Participants randomized into Arm B, clinical standard of care will be followed with no intervention provided using the MR-Stride Plus. Participants will also complete the 6MWT at screening, baseline and biweekly post-discharge from acute care and at days 45 and 90 (+/-7 days) following discharge.
 
All participants will be followed for 90 days following discharge from acute care facility for initial stroke event and discharge date, discharge setting, number of physical therapy services and occurrence of readmission to acute care will be collected.

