Minimizing Bias	The study is not blinded because the primary outcome measure of gait speed renders the likelihood of a placebo benefit unlikely. However, Study Participants will be blinded to the results of the 6-meter walk test (approximately 20 feet). No results will be provided to the Study Participant at any time during participation in the trial.
Study Visits	All key assessments will be conducted at the study site and remotely via telecommunication, as applicable.
Study Duration	Each Participant is required to complete a screening visit. For Participants who are randomized into Arm A (MR-Stride Plus Intervention), therapy sessions will take approximately forty-five (45) minutes for set-up and therapy. After the first therapy session in

	
the acute care setting, participants should be able to complete the setup and therapy session with the MR-Stride Plus independently. Collection of data related to study adherence (for participants in the MR-Stride Plus Intervention), gait speed assessment, standard of care administration, discharge and readmission will be performed by study staff remotely through review of medical records, MR-Stride Plus database, and by contacting the participant over the phone. Once participants have reached 90 days following discharge from the acute care facility for the initial stroke event, no follow-up or subsequent Participant involvement is required.

Study Discontinuation, Drop Out, Withdrawal and Replacement	
Participants may discontinue their participation in the study at any time. A Participant may be withdrawn from the study at any time at the discretion of the Investigator.
 
Participants who are withdrawn or drop out prior to the study endpoint will still have data that was collected up until the withdrawal/drop out eligible for analysis. These Participants will be analyzed in an Intent-To-Treat analysis.

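### The protocol both requires and makes optional the Day 90 gait-speed assessment of Arm A participants who stop Stride Plus, so that value can be missing selectively in one arm

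*Protocol*

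**What the plan says.** All references are to the Protocol.

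- **Study Design, Post-Intervention Phase (Arm A).** "Participants will be followed from discontinuation of the Stride Plus until Day 90". It continues: "At Day 90 (+7 days), participants will complete a walking test using the Stride Plus to determine walking speed". Both are stated as things that will happen.
- **Procedures, Arm A.** Participants who cannot keep the therapy schedule are contacted. Then "At investigator discretion and participant agreement, the number of sessions a week may be reduced or the participant may withdraw from therapy". For anyone withdrawn from therapy, "participants will be asked if they are willing to participate in a gait speed assessment using the MR-Stride Plus" at Days 45 and 90, where these are still outstanding. The same section schedules the 6-meter walk every two weeks to study completion, and adds a gait-speed assessment at "the time of withdrawal from study therapy if withdrawal occurs before Day 90 (+/-7) post discharge".
- **Procedures, Arm B.** The walk test is scheduled every two weeks after discharge and at Days 45 and 90, with no willingness condition.
- **Primary Endpoint.** Change in gait speed runs from baseline to study completion, meaning 90 days after discharge, or sooner for a participant who withdraws. It does not say from what.
- **Study Discontinuation, Drop Out, Withdrawal and Replacement.** "A Participant may be withdrawn from the study at any time at the discretion of the Investigator". Data gathered up to that point remain eligible, and these participants enter an intent-to-treat analysis.
- **Data Analysis.** Intent-to-treat covers everyone enrolled, withdrawn or incomplete cases included, provided an analysis is possible.

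**The concern.** An intent-to-treat comparison of gait speed at Day 90 needs the Day 90 measurement from people who stopped the device as well as from those who continued. The protocol gives sites two instructions for the former: obtain the measurement, or ask whether the participant would mind giving it. A site following the second complies with the protocol and may still have no Day 90 value.

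The optional route is not spread evenly. It opens only in Arm A, it follows a failure to keep the therapy schedule, and the step to therapy withdrawal involves investigator discretion in an unblinded trial. Adherence may well be related to outcome, so the missing values need not resemble the observed ones. If the undefined withdrawal in the primary endpoint is read as withdrawal from therapy, a site could also treat study completion as reached when the device is stopped. That would end the biweekly walks too, and shorten observation for the second primary endpoint, time to functional change in gait speed, in Arm A only.

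**Working it through.** **1. Do the two passages govern the same person?** Yes. Therapy in Arm A is planned to run to Day 90, so the Post-Intervention Phase has any length only for someone who stops early. That is the person the willingness sentence in Procedures addresses. Both passages concern a walk measured with the Stride Plus, so a difference of instrument does not explain the conflict. For someone who stops at, say, Day 30, the Day 90 test is required by one passage and optional under the other.

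**2. Does other text settle it?** Not fully.
- The biweekly 6-meter walk runs to study completion, but the primary endpoint lets completion come early on an undefined withdrawal.
- The test at therapy withdrawal gives a value, but not a Day 90 value.
- The closing sentence of Procedures follows all participants for 90 days, but the items it lists are discharge, physical therapy and readmission data, not gait speed.

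**3. How large could the effect be?** The protocol states about 40 participants, expected to split 20/20. It gives no SD, effect size or dropout rate, so there is no planned figure to reproduce. What follows is illustration with assumed inputs. Let d be the share of Arm A that stops and has no Day 90 value.

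*(a) These participants are left out.* Overstatement of the Arm A mean gain = d × g, where g is the shortfall in their 90-day gain against those who continue.
- d = 2/20 = 0.10, g = 0.05 m/s: 0.10 × 0.05 = 0.005 m/s
- d = 5/20 = 0.25, g = 0.10 m/s: 0.25 × 0.10 = 0.025 m/s
- d = 8/20 = 0.40, g = 0.20 m/s: 0.40 × 0.20 = 0.08 m/s

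*(b) The value at therapy withdrawal stands in for Day 90.* Understatement = d × 0.5 × G, where G is their 90-day gain, assumed half reached at withdrawal.
- d = 2/20 = 0.10, G = 0.1 m/s: 0.10 × 0.5 × 0.1 = 0.005 m/s
- d = 4/20 = 0.20, G = 0.2 m/s: 0.20 × 0.5 × 0.2 = 0.02 m/s
- d = 6/20 = 0.30, G = 0.3 m/s: 0.30 × 0.5 × 0.3 = 0.045 m/s

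The upper ends use different shares. At a common d = 0.30, the largest values are 0.30 × 0.20 = 0.06 m/s for (a) and 0.045 m/s for (b).

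**4. Scale.** With 20 per arm, two-sided 5% and 80% power, the detectable difference is (1.96 + 0.84) × SD × √(1/20 + 1/20). For an assumed SD of 0.15 to 0.25 m/s this is 0.13 to 0.22 m/s. The low end of either bias is negligible against that; the high end is not.

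**The case against.** The strongest reply is that little is lost. Gait speed is measured when therapy stops, the biweekly 6-meter walk has no willingness condition, the endpoint allows an earlier value, and withdrawn participants stay in the intent-to-treat analysis. The willingness sentence covers only the device-based assessments at Days 45 and 90, and any participant may decline any assessment anyway. How missing Day 90 values are handled belongs in the SAP, which is not at hand.

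Much of this stands, and it rules out several stronger readings:

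- *Poor adherers drop out of the primary comparison.* The documents do not support this. At most the Day 90 value is lost; a participant leaves the analysis only if no usable value exists.
- *The loss favours the device.* That follows only if these participants are excluded. If the withdrawal value is used, Arm A can be understated.
- *The investigator-withdrawal clause is a third, conflicting rule.* It is a general clause on leaving the study and applies to both arms. It neither contradicts the other two passages nor makes the problem one-sided. Its weakness is only that it does not distinguish leaving the study from stopping therapy.

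What the reply does not remove is the conflict itself. The freedom to decline is common to both arms; writing the assessment as optional for one arm's poor adherers is not. An SAP can model missing values, but cannot recover measurements that sites were not required to seek.

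**Conclusion.** The point holds in a limited form. Study Design and Procedures contradict each other on whether gait speed must be sought to Day 90 after Stride Plus is stopped, the optional version applies to Arm A alone, and the primary endpoint leaves the meaning of withdrawal open. Day 90 gait speed can therefore be missing selectively in Arm A, with no determinate direction of bias: about 0.005 to 0.08 m/s too high if those participants are omitted, or about 0.005 to 0.045 m/s too low if an earlier value is used. These sizes rest wholly on assumed stopping shares, gaps and recovery. Case (b) also assumes that gait speed keeps improving after therapy stops; if it fell, the sign would reverse. No size was worked out for the time-to-change endpoint. The correction is worth making because the loss is avoidable and cannot be repaired at analysis.

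**What to change.** Four wording changes:

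1. **Study Design and Procedures, Arm A.** Reconcile them so that participants who stop Stride Plus stay in the study on the same gait-speed schedule to Day 90 as Arm B. They remain free to decline any assessment, and each refusal is recorded.
2. **Procedures, Arm A.** Replace the sentence that asks about willingness with a reference to that common schedule.
3. **Primary Endpoint.** State that withdrawal there means leaving the study, not stopping therapy.
4. **Study Discontinuation, Drop Out, Withdrawal and Replacement.** State that stopping therapy is not by itself withdrawal from the study.

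The rules on when therapy is stopped, and the investigator's discretion to withdraw a participant from the study, are left as they are; curtailing that discretion would go further than the contradiction requires. The Day 45 and Day 90 contacts and the biweekly walks are already planned, so the cost is a wording amendment and some follow-up calls to participants who have lost interest.

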Primary Endpoint	
The primary study objectives are as follow:
 
 1) Change in gait speed (m/s) from baseline to study completion (90 days following discharge from acute care or earlier if study participant withdraws); 2) time-to-functional change in gait speed from baseline to study completion 3) adherence to the MR-Stride Plus therapy schedule.
Secondary Endpoint	
The secondary study objective is to assess the median length of stay in acute stroke hospital and the percent of readmission during the 90 (+/-7) days following discharge.

Participant Population	
No age, race, education or geographical restrictions apply. All individuals who meet the inclusion/exclusion criteria at participating study sites will be considered.

Inclusion Criteria	
To be enrolled and randomized into the study, potential Study Participants must meet all of the following inclusion criteria:
 
 1.0 Must be 18 years of age or older. 2.0 Must be able to read and speak English fluently. 3.0 Be within 24 hours from admission for confirmed stroke event.

	
4.0 Currently able to walk at a speed greater or equal to 0.4m/s, but less than 1.0m/s, as determined by a 6-meter walk test (approximately 20 feet) for comfortable walking speed (the average of three trials).
 
5.0 Demonstrates some level of asymmetry in gait.
 
6.0 Is expected to be discharged from the acute care setting requiring physical therapy per standard of care and participant has verbally committed to receiving at least one therapy session.
 
7.0 Able and willing to consent with proposed study schema (verbal commitment), including consent to participate in communication with the treating clinician (as needed) during the study period.
 
8.0 Score ≤1 on question 1b and a 0 on question 1c on the NIH Stroke Scale.
 
9.0 Able to safely participate in protocol-defined walking therapy sessions of 30-minute duration as determined by the Investigator.

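### The two arms' gait-speed tests run on different clocks and Arm A's instrument is unsettled, so time to functional change is read on unmatched visits

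*Protocol*

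**What the plan says.** Primary endpoint 2 is "time-to-functional change in gait speed from baseline to study completion". Endpoint 1 is the change in gait speed to study completion, defined as "90 days following discharge from acute care or earlier if study participant withdraws".

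The assessments behind these endpoints are set out in three places.

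- **Procedures, Arm A:** "The 6-meter walk test (approximately 20 feet) will be conducted to evaluate gait speed at screening and biweekly thereafter until study completion". Gait speed is also assessed when a participant withdraws from study therapy. Those who withdraw are asked to take device-based assessments at Days 45 and 90 if these have not been done already.
- **Procedures, Arm B:** "Participants will also complete the 6MWT at screening, baseline and biweekly post-discharge from acute care and at days 45 and 90 (+/-7 days". The abbreviation 6MWT is not defined; it is read here as the 6-metre test.
- **Study Design:** for Arm B, "Participants will complete a 6-meter walk test (approximately 20 feet) to measure gait speed at baseline, biweekly post- discharge from acute care", continuing to Day 90, with no Day 45 test. For Arm A this section lists only walking tests with the Stride Plus, at discontinuation and at the end: "At Day 90 (+7 days), participants will complete a walking test using the Stride Plus to determine walking speed". It lists no post-baseline 6-metre test for Arm A.

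Three other statements bear on the point. Inclusion criterion 4 requires a gait speed in a set range, "as determined by a 6-meter walk test (approximately 20 feet) for comfortable walking speed (the average of three trials", so everyone has a 6-metre value at screening. Study Design says of the period after discharge: "Participants will not be required to physically visit the study facility for study-specific procedures". Study Duration names the MR-Stride Plus database among the sources for remotely collected data, which include gait speed. Biweekly is not defined anywhere.

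**The concern.** A change in gait speed can be recorded only at a test. The recorded time is the first test after the change, so it depends on recovery and also on the dates of the tests. If those dates differ by arm, two groups with identical recovery can show different recorded times. The trial is unblinded, and matched assessment is one of the protections it can still offer.

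The instrument matters as well. If Arm A's last value is a Stride Plus reading and Arm B's is a 6-metre test, any systematic offset between the two methods becomes part of the treatment difference in endpoint 1.

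**Working it through.** The protocol gives no alpha, effect size, SD, length of stay or threshold for functional change, so there is no planned figure to reproduce. Every numerical input below is assumed unless a source is named.

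**1. Schedules side by side**

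| | Arm A | Arm B |
|---|---|---|
| Start of biweekly clock | Screening (Procedures) | Discharge (Study Design, Procedures) |
| Day 45 6-metre test | None named | In Procedures, not in Study Design |
| Test at therapy withdrawal | Yes | Cannot arise |
| Stride Plus walking tests | Discontinuation, Day 90 (Study Design) | None |

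**2. Test days for one participant.** Take a 5-day stay and 14-day spacing, and count from screening, so completion is day 5 + 90 = 95.

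- Arm A: 14, 28, 42, 56, 70, 84, 95.
- Arm B: 5 + 14 = 19, then 33, 47, 50 (that is, 5 + 45), 61, 75, 89, 95.

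A change on day 10 is recorded on day 14 in Arm A and day 19 in Arm B. A change on day 15 is recorded on day 28 in Arm A and day 19 in Arm B. For an error-free change on each of days 1 to 95:

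- Arm A records it first on 56 days, always by 5 days.
- Arm B records it first on 33 days: by 9 days on 25 of them and by 6 days on 8.
- Both record it on the same day on the remaining 6.

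The mean lead for Arm A is (56×5 − 25×9 − 8×6)/95 = 7/95 = 0.07 days. Averaged over all days the grids almost cancel. The distortion therefore depends on when changes cluster.

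**3. Null simulation, identical recovery in both arms.** The model is:

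- observed change at day t = gain × (1 − exp(−t/30)) + test error;
- gain is normal, with mean 0.30 (SD 0.15) or 0.20 (SD 0.10) m/s;
- test-error SD is 0.05 m/s at baseline and at each follow-up;
- stay is Poisson with mean 3, 5 or 7 days (minimum 1);
- 20 per arm, as the protocol expects;
- 6-metre tests only, 14-day spacing and no withdrawals;
- the event is the first observed change at or above the threshold, tested by log-rank with |z| > 1.96.

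There were 4,000 trials per cell, with a Monte Carlo standard error of about 0.4 points. Entries are for mean stays of 3/5/7 days.

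| Gain, threshold (m/s) | False positives, % | Median, B minus A, days |
|---|---|---|
| 0.30, 0.10 | 11.5 / 9.0 / 8.1 | 2.0 / 3.6 / 5.6 |
| 0.30, 0.16 | 5.4 / 5.6 / 5.6 | 0.3 / 0.3 / 0.7 |
| 0.30, 0.20 | 5.6 / 5.6 / 5.9 | −0.4 / 0.2 / 0.4 |
| 0.20, 0.10 | 6.5 / 5.8 / 4.9 | 0.8 / 0.9 / 1.6 |
| 0.20, 0.16 | 5.4 / 5.7 / 6.6 | −1.5 / −1.3 / −0.7 |
| 0.20, 0.20 | 5.2 / 5.4 / 5.4 | −5.0 / −4.9 / −5.1 |

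A common schedule gives 4.9 to 6.1% over all 18 cells. In the first row 10.9/8.4/7.0% favour Arm A. In the last row 3.5/4.0/4.2% favour Arm B and 1.8/1.4/1.3% favour Arm A. In that row only about 65% reach the threshold, and a median is undefined in 10 to 11% of trials.

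**4. What drives the first row.** Start Arm A's clock at discharge and change nothing else, so that Arm B keeps its extra Day 45 test. The rates fall to 5.7/5.5/4.2% (1,500 trials per cell); a separate run gave 5.2 to 6.0%. The clock origin is the cause. The Day 45 difference adds nothing detectable.

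**5. Sensitivity**

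- *Analysis.* An interval-censored log-logistic likelihood-ratio test brings the first row to 5.3/5.7/4.7%, against 5.2/5.5/4.7% on a common schedule.
- *Twice-weekly spacing (3.5 days).* At threshold 0.10 the rates are 6.3/7.2/11.7% (gain 0.30) and 5.7/5.7/8.3% (gain 0.20). The other 12 cells run from 4.3 to 6.1%.
- *A different model.* With exponential times to change and the same stay of 3, 5 or 7 days for everyone, false positives are 12.5 to 21.2% for a true median of 14 days and 5.1 to 7.3% for 30 days. A matched grid gives 5.2 to 6.0%.

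**6. Endpoint 1, if Arm A's final value were the device reading.** Assume an offset of 0.05 m/s between methods, 20 per arm and a two-sided t-test with 38 degrees of freedom. The noncentrality is 0.05/(SD × √(2/20)). For an SD of change of 0.20 it is 0.79, with a false-positive rate of 12.0%. For an SD of 0.15 it is 1.05, with a rate of 17.7%.

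**The case against.** The strongest reply is that the measured effect is narrow. Fifteen of the 18 scenarios are close to nominal, and the average shift over all days is 0.07 days. The protocol gives no threshold, gain, stay or test error, so nothing shows that the early-change scenario is the relevant one. The inflation also presumes a log-rank test on first-observed dates. The protocol does not name that analysis, and a SAP could choose an interval-censored one. All of this stands, and it limits what can be claimed about size.

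It does not remove the point. Visit dates are protocol content. An interval-censored analysis can protect the test, but it cannot restore visits that were not held or put observed times and medians on one grid.

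A reader might infer from the missing Day 45 6-metre test that Arm A needs one. The calculation does not support that for endpoint 2 in the scenario where the inflation arises: moving the clock was enough. A reader might also want a new test at study withdrawal in both arms. Nothing computed here supports that, and it may be unobtainable where no facility visit is required.

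**Conclusion.** The point holds as a conflict in the schedule and the instrument. As written, the 6-metre clocks start at screening in Arm A and at discharge in Arm B. The Arm B schedule differs between Study Design and Procedures, and Study Design gives Arm A only device tests. Endpoint 2 is therefore observed on unmatched visits. Under the assumed models the false-positive rate is materially raised when change comes early and is near nominal when it comes later.

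Two stronger readings are tempting, and the documents support neither. One is that the schedule systematically favours Arm A. The excess does favour Arm A where change comes early, but the direction reverses in other scenarios and the protocol supplies none of the inputs. The other is that endpoint 1 compares different instruments. The protocol does not say that Arm A's final value is the Stride Plus reading, and Procedures gives Arm A 6-metre tests until completion. Since all participants have a screening 6-metre test, endpoint 1 can be made comparable. It is exposed because the protocol leaves the source open, and that deserves the same attention as the visit grid.

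This should be corrected. Confidence is high in the textual conflict and medium in its effect.

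**What to change.** Reconcile Study Design with both Procedures subsections:

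- Give both arms the 6-metre test on one clock, for example biweekly from discharge to Day 90 (±7 days). Either hold the Day 45 test in both arms or leave it out of endpoint 2.
- Say whether biweekly means every two weeks or twice a week, and write out 6MWT.
- Use the screening 6-metre test as baseline in both arms.
- State that endpoints 1 and 2 use 6-metre tests only, done the same way in both arms after discharge, and that Stride Plus readings are descriptive.
- Leave the therapy-withdrawal reading, which only Arm A can have, out of endpoint 2.

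No new study-withdrawal test is needed. The cost is protocol wording, a decision on how the 6-metre test is done without facility visits, slightly coarser event timing in Arm A and, if Day 45 is kept, one extra 6-metre test there. The change has to be made before the visits take place.
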